Overall Study Coordinators (at UNC)	Alliance Foundation Trials (AFT)	Principal Investigator

General email: [contact]
 
[name] [contact] [contact]
 
[name] [contact] [contact]
 
[name] [contact] [contact]
	
[name] [contact]
	
[name] University of North Carolina [contact]
 
Administrator: [name] [contact] [contact]

This document contains confidential information of Alliance Foundation Trials, LLC. The information in this document cannot be used for any purpose other than the evaluation or conduct of the clinical investigation without the prior written consent of Alliance Foundation Trials, LLC.

[figure not shown]
I. Synopsis and Study Schema

Study Title	Electronic patient reporting of symptoms during outpatient cancer treatment: A U.S. national randomized controlled trial
Study Acronym	PRO-TECT: P atient- R eported O utcomes t o E nhance C ancer T reatment trial
Study Number	AFT-39
Study Type/Phase	RCT (not a drug trial)
Number of Study Patients	1,200 patients, from 50 (+/- 5) U.S. sites
Estimated Duration of Study	Each patient participates for up to 12 Months
Anticipated Recruitment Start Date	August 1, 2017
Rationale	Symptoms are common during cancer treatment, but frequently go undetected by clinicians between visits. Patient self-reporting of symptoms online (or automated telephone systems), with alerts to clinicians for severe symptoms, offers a potential approach to flag concerning symptoms and prevent downstream complications. A prior single-center RCT provided initial evidence of improved clinical outcomes and reduced ER visits using such an approach. The current study is designed to test nationally whether patients' outcomes and utilization of services can be improved through symptom monitoring via patient-reported outcomes between visits.
Study Objective and Outcomes	The objective is to determine whether systematic monitoring of symptoms via patient-reported outcome measures during routine cancer care delivery improves meaningful clinical outcomes. The principal (primary) outcome is overall survival. Secondary outcomes include physical functioning/ health-related quality of life/financial burden/symptom burden, emergency room/hospital utilization, duration of cancer treatment, and patient satisfaction/communication.
Qualitative and Implementation Objectives and Outcomes	Elicit perspectives about benefit-burden tradeoffs for integrating patient-reported outcomes into clinical workflow from different stakeholders, including patients, clinicians, site staff, and representatives of patient and professional organizations. Identify barriers, facilitators, and strategies used by practices to integrate patient-reported outcomes into clinical workflow. Analysis of financial impact.
Trial Design	“Cluster” RCT, randomization unit: oncology practice site (approximately 50 sites randomized in a 1:1 ratio to the “control” arm or “intervention” arm).
Site Requirements for Participation in Trial	
 • Lead CRA • Clinical nursing staff champion (“Nurse Champion”) for the study.
Participant Payments	
 • \$150 gift card (\$75 at baseline and \$75 at 3 months) • Mailed directly to patient participants by UNC

Patient Inclusion Criteria	
• Adults (21+) with metastatic cancer of any type (EXCEPT leukemia or indolent [slow growing] lymphoma)• Receiving outpatient systemic cancer treatment with palliative/non-curative intent (e.g., chemotherapy, targeted therapy, or immunotherapy)• Patients can be enrolled at any point in their cancer treatment trajectory (i.e., not just at initiation of first-line treatment)• Understands English, Spanish, or Mandarin Chinese
Patient Exclusion Criteria	
• Cognitive deficits that would preclude understanding of consent form and/or study questionnaires• Current participation in a therapeutic clinical trial• Patients being treated with curative intent (e.g., adjuvant chemotherapy for breast, lung, or ovarian cancer; primary curative therapy for testis cancer or lymphoma)• Receiving hormonal therapy only (e.g., tamoxifen or aromatase inhibitors in breast cancer; androgen deprivation therapy in prostate cancer; or octreotide in neuroendocrine cancers; ibrance/palbociclib)• Indolent/slow-growing lymphoma (due to their prolonged time courses that may be minimally symptomatic)• Leukemia of any type• Does not understand English, Spanish, or Mandarin Chinese


Study Procedures
	
PROCEDURES AT ALL SITES (CONTROL SITES AND INTERVENTION SITES):
 
• Site staff (CRA and Nurse Champion required) will attend the site initiation webinar with UNC staff, including training for the PRO-Core online data management system and orientation to the symptom management guidelines.• At enrollment, all participants will be given a booklet with patient-level symptom advice and a link to the content online.• All participants will receive \$150 for participation (\$75 at baseline and \$75 at 3-months), mailed to them as gift cards by UNC.• CRAs will train all participants how to complete outcomes questionnaires for the trial using the PRO-Core online system. Participants will be given a choice to complete these in clinic or from home online, or if necessary via paper in clinic (with the CRA entering the data into PRO-Core). If the patient does not self-complete this information, the CRA will contact them to collect the information and then enter it into PRO-Core. The outcomes questionnaires will be completed at baseline; and at month 1 (+/- 2 weeks); and at months 3, 6, 9, and 12/off-study (+/- 4 weeks each), and will be available in English, Spanish, or Mandarin Chinese. At each time point, the CRA will contact the participant to remind them about the upcoming questionnaire and offer help.• Chart abstraction will be conducted by CRAs at baseline and at off-study for each participant, with data entered into the PRO-Core system. Date of death information will additionally be abstracted at 18 and 24 months, and possibly later per the UNC study team.• CRAs will be asked to complete a feedback survey (entered by the CRA into the PRO-Core online system) and may be asked to participate in a brief telephone debriefing and/or site visit.• Accrual will be monitored in a weekly teleconference between the UNC team and site CRAs.• At completion of the study, sites may be offered the PRO Core system for broad implementation at their site. 
ADDITIONAL PROCEDURES AT INTERVENTION SITES ONLY:
 
• At baseline, CRAs will also train patients to self-report symptoms, financial burden, and physical functioning using the PRO-Core system weekly for up to a year, with a choice to do this online or via an automated telephone system (patient choice), and a choice of English, Spanish, or Mandarin Chinese.• Whenever a concerning issue is reported, an automated “email alert” notification will be sent to the site CRA. The CRA will forward the email alert to the responsible clinical nurse (or other covering clinician) and CC the site’s Nurse Champion. Within 72 hours, the CRA will document what action(s), if any, were taken by the nurse in response to the alert (entered by the CRA into a form in the PRO-Core system).• A PRO report will be printed/generated by the site CRA whenever the patient has a clinic visit and will be given to the oncologist and nurse caring for the patient.

1.1. Overview and Rationale

Symptoms are common among patients receiving treatment for advanced cancers and are a major cause of distress, functional disability, and emergency room/hospital utilization^{1,2,3} but go undetected and unaddressed by clinicians up to half the time.^{4,5,6,7} There is substantial and growing national interest to integrate electronic patient-reported outcomes (PROs) into routine practice to improve detection and management of symptoms.^{8,9,10} However, the value of integrating PRO collection into routine care, acceptability to patients and clinicians, and the required infrastructure and resource needs are uncertain.^{11,12,13}

Multiple studies, largely at single centers, have reported associations between routine collection of electronic PROs (e.g. symptoms reported by patients using tablets or automated telephone systems, either between visits or at visits) with improved efficiency of symptom assessment, patient-clinician communication, and satisfaction as well as symptom control, well-being, reduced emergency room utilization, longer duration of chemotherapy treatment, and improved survival.^{14,15,16,17,18,19,20,21} Although this body of work suggests benefits, it is not yet definitive because a large, rigorous, multi-center controlled trial has not been conducted.

Therefore, this national multicenter cluster-randomized trial is being conducted to determine whether systematic monitoring of symptoms via PROs during routine cancer care delivery improves meaningful clinical outcomes: the “Patient-Reported Outcomes to Enhance Cancer Treatment” trial (“PRO-TECT”). The design of this trial is based on a prior large single center RCT (N=766) showing significant clinical benefits of a similar approach.¹⁴

1.2. Brief Description of Study Design and Intervention

This is an RCT in up to 50 (+/- 5) sites where randomization will occur in a 1:1 ratio at the site level (not at the individual patient level). Therefore, approximately 25 sites will be randomized to the PRO-TECT intervention arm (patient-reporting of symptoms plus access to a standardized symptom management guideline), and approximately 25 sites will be randomized to the control arm (usual care delivery plus access to a standardized symptom management guideline). Specifically:

PROCEDURES AT ALL SITES (CONTROL SITES AND INTERVENTION SITES):

- Site staff (CRA and Nurse Champion required) will attend the site initiation webinar with UNC staff, including training for the PRO-Core online data management system and orientation to the symptom management guidelines.
- At enrollment, all participants will be given a booklet with patient-level symptom advice and a link to the content online.
- All participants will receive \$150 for participation (\$75 at baseline and \$75 at 3-months), mailed to them as gift cards by UNC.
- CRAs will train all participants how to complete outcomes questionnaires for the trial using the PRO-Core online system. Participants will be given a choice to complete these in clinic or from home online, or if necessary via paper in clinic (with the CRA entering the data into PRO-Core). If the patient does not self-complete this information, the CRA will contact them to collect the information and then enter it into PRO-Core. The outcomes questionnaires will be completed at baseline; and at month 1 (+/- 2 weeks); and at months 3, 6, 9, and 12/off-study (+/- 4 weeks

each), and will be available in English, Spanish, or Mandarin Chinese. At each time point, the CRA will contact the participant to remind them about the upcoming questionnaire and offer help.

- Chart abstraction will be conducted by CRAs at baseline and at off-study for each participant, with data entered into the PRO-Core system. Date of death information will additionally be abstracted at 18 and 24 months, and possibly later per the UNC study team.
- CRAs will be asked to complete a feedback survey (entered by the CRA into the PRO-Core online system) and may be asked to participate in a brief telephone debriefing and/or site visit.
- Accrual will be monitored in a weekly teleconference between the UNC team and site CRAs.
- At completion of the study, sites may be offered the PRO Core system for broad implementation at their site.

ADDITIONAL PROCEDURES AT INTERVENTION SITES ONLY:

- At baseline, CRAs will also train patients to self-report symptoms, financial burden, and physical functioning using the PRO-Core system weekly for up to a year, with a choice to do this online or via an automated telephone system (patient choice), and a choice of English, Spanish, or Mandarin Chinese.
- Whenever a concerning issue is reported, an automated “email alert” notification will be sent to the site CRA. The CRA will forward the email alert to the responsible clinical nurse (or other covering clinician) and CC the site’s Nurse Champion. Within 72 hours, the CRA will document what action(s), if any, were taken by the nurse in response to the alert (entered by the CRA into a form in the PRO-Core system).
- A PRO report will be printed/generated by the site CRA whenever the patient has a clinic visit, and will be given to the oncologist and nurse caring for the patient.
- At completion of the study, sites may be offered the PRO Core system for broad implementation at their site.

1.3. Study Objective and Outcomes

The objective of this study is to determine whether systematic monitoring of symptoms via patient-reported outcomes (PROs) during routine cancer care delivery improves meaningful clinical outcomes, including survival, quality of life, symptom control, emergency room visits, duration of chemotherapy administration, and patient satisfaction with care. The principal (primary) outcome for the analysis is overall survival. The secondary outcomes include physical functioning/health-related quality of life/symptom burden, emergency room/hospital utilization, duration of cancer treatment, and patient satisfaction/communication.

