- **Patient Quality of Life Questionnaire (Questionnaire P2) – ALL SITES:** The outcomes of physical functioning, health-related quality of life, and symptom control will be assessed by items from the “EORTC-QLQ-C30”, which will be administered to each patient participant in the “Patient Quality of Life Questionnaire” (Form P2) at baseline; at month 1 (+/- 2 weeks); at months 3, 6, 9; and at month 12/off-study (+/- 4 weeks each). The EORTC QLQ-C30 is a well-established and frequently used questionnaire^{22,23,24} that includes a 5-item physical functioning domain, individual symptom items corresponding to the symptoms in the PRO intervention system, and a composite quality of life score.^{22,23,24} The QLQ-C30 has been rigorously tested for its psychometric properties in qualitative and quantitative studies and has been widely used in clinical studies in oncology, and is a standard measure used across oncology drug development trials and in many ALLIANCE national clinical trials.
- **Patient Satisfaction Questionnaire (Questionnaire P3) – ALL SITES:** This questionnaire will be administered to each participant at baseline and 3 months of participation (+/- 4 weeks for the month 3 form). The satisfaction questions are from the Consumer Assessment of Healthcare Providers and Systems (CAHPS) survey system, which is maintained by the Agency for Healthcare Research and Quality (AHRQ) to support and promote the assessment of consumers' experiences with health care,²⁵ and from the “Patient-Centered Communication in Cancer Care” short form questionnaire (PCC-CA-6).²⁶ Participants or their designated caregivers may also be contacted by UNC for follow up questions about their responses.
- **Patient PRO Feedback Questionnaire (Questionnaire P4) – INTERVENTION SITES ONLY:** In the intervention arm only, this questionnaire will be administered to patients after 3 months of participation (+/- 4 weeks). This questionnaire includes items about the ease and perceived value of using the PRO system. This information will be useful for dissemination and future implementation efforts. Understanding these perspectives is essential to avoid unnecessary burden and to optimize convenience and benefits.

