For the trial's secondary analyses, emergency room/hospital utilization and duration of cancer treatment will be compared between arms using stratified Fine-Gray competing risk regression with death as a competing event (stratified by cancer type, with robust sandwich covariance matrix estimates to account for site clustering). Physical function/health-related quality of life/symptom burden/financial burden as measured by the QLQ-C30 at 3 months and patient satisfaction/communication as measured by CAHPS items will each be compared between arms using a general linear mixed model approach including a fixed effect for cancer type, a random effect for site, and a continuous covariate for the corresponding baseline score. All other quantitative outcomes will be tabulated within arms descriptively (see below for separate description of qualitative analyses). While a focus of the non-survival assessments is the 3-month time point, analyses will include each post-baseline assessment time point (1, 6, 9, and 12 months) as well as longitudinal analyses incorporating all post-baseline PRO data. Supplemental analysis will also include multivariable analysis of each primary outcome including the following covariates: age (<60 versus \geq 60), gender (female versus male), race/ethnicity (white non-Hispanic versus other), education status (high school graduate/GED or less versus some college or more), disease type (e.g., gastrointestinal, genitourinary, gynecologic, breast, lung/head and neck, melanoma, versus other), prior computer/email/internet use (rarely or less versus sometimes or more), and oncology practice site location (predominantly urban/suburban vs rural). Subgroup analyses may also be conducted for each of these covariates. For patients who die, have missing data, or go off study before the time point of analysis, prior or off study data (whichever is later) may be carried forward. Similar to above, sensitivity analyses may be carried out with truncation of data at March 1, 2020, to assess for impact of COVID.

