### 3. Statistical methods for analysis

#### 3.1. Data handling conventions

##### 3.1.1. EORTC QLQ-C30 and CAHPS scoring algorithms

The EORTC QLQ-C30 contains 30 questions that assess various domains of HRQL. Scoring for the EORTC QLQ-C30 can be found in the Scoring Manual available from the EORTC. The standard scoring of the EORTC QLQ-C30 generates scales or item scores. Gundy CM, et al. (2012) described additional composite scales. In planned analyses, Physical Functioning is based on Q1-5; Symptom Burden (“Control”) is based on 8 symptom scales/items (Q8-19); Health-Related Quality of Life is based on 5 functional scales and 8 symptom scales/items (Q1-27); Fatigue is based on Q10, Q12, & Q18; Nausea and Vomiting on Q14 & Q15; Pain on Q9 & Q19; Dyspnea on Q8; Insomnia on Q11; Appetite Loss on Q13; Constipation on Q16; and Diarrhea on Q17. Analysis of QALYs will additionally compute health utilities from EORTC QLQ-C30 data using the algorithm for U.S. patients published by Revicki DA, et al. (2021).

Items from the CAHPS survey were additionally administered. These items will be analyzed as individual items and no scoring algorithm will be applied to combine items into scale scores.

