### 3.6. Secondary and exploratory endpoint evaluation

#### 3.6.1. Secondary and exploratory endpoints

As described above, the key secondary endpoint is physical function at 3 months as measured by the EORTC QLQ-C30 Physical Function Scale. Additional secondary endpoints include: EORTC QLQ-C30 symptom burden (control) score at 3 months, and EORTC QLQ-C30 HRQL score at 3 months.

Additional endpoints include: EORTC QLQ-C30 appetite loss, constipation, diarrhea, dyspnea, fatigue, insomnia, nausea/vomiting, and pain score at 3 months; EORTC QLQ-C30 function scales at 3 months, patient adherence to the intervention (i.e., completion of the weekly symptom surveys); CAHPS item scores at 3 months; emergency room visits; alert notification; and financial toxicity.

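### PCC-CA-6 is collected in both arms for the satisfaction/communication outcome, but neither document plans a between-arm comparison of it, and under the SAP no instrument gives a modelled estimate for communication

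*Protocol*

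**What the plan says.** The protocol synopsis and section 1.3 treat satisfaction and communication as one combined secondary outcome; 1.3 closes its list with "duration of cancer treatment, and patient satisfaction/communication".

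Protocol 5.5.1 describes Form P3, used at all sites, as drawing on CAHPS and on a patient-centered communication "short form questionnaire (PCC-CA-6"), which has its own citation (reference 26). On timing it says: "This questionnaire will be administered to each participant at baseline and 3 months of participation". The schedule tables and their footnote add month 12.

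Protocol 7.1 then fixes the measure and the method: "patient satisfaction/communication as measured by CAHPS items will each be compared between arms using a general linear mixed model approach". The model has a fixed effect for cancer type, a random effect for site and the baseline score as covariate. PCC-CA-6 is not named. The same section has a catch-all: "All other quantitative outcomes will be tabulated within arms descriptively".

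The SAP objective (2.2.1) keeps satisfaction with care and does not name communication. On the P3 content, SAP 3.1.1 says only "Items from the CAHPS survey were additionally administered" and rules out combining those items into scales. SAP 3.6.1 places among the additional endpoints "CAHPS item scores at 3 months; emergency room visits; alert notification; and financial toxicity". SAP 3.6.3 describes CAHPS items by the frequency of each response. SAP Section 4, on changes from the protocol, covers subgroups and the survival model only.

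**The concern.** Better communication between patients and clinicians is one of the benefits that protocol 1.1 cites from earlier work, and protocol 8.5 repeats it as a possible benefit to participants. The protocol made it part of a named secondary outcome and asked patients in both arms to complete an instrument built for it. A reader would expect that instrument to have a scoring rule and a comparison between arms. It has neither.

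The loss comes in two steps. Protocol 7.1 narrows the measure to CAHPS items but keeps a model-based comparison. The SAP then drops communication by name and replaces the CAHPS model with frequencies. Someone who follows the SAP exactly will report no effect estimate, no confidence interval and no allowance for clustering for this half of the outcome. Because the data exist without a plan, any later analysis of them would be open to the question of why it was chosen.

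**Working it through.** The plan states no power or sample-size figure for communication, so there is none to reproduce. The check traces the outcome through the documents.

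1. **Named as an outcome?** Yes: protocol synopsis and 1.3, jointly with satisfaction.
2. **Instrument in both arms?** Yes according to protocol 5.5.1: PCC-CA-6 within Form P3, at all sites. The schedule tables do not confirm it. They list the P3 content as CAHPS questions at control sites and as questions about the PRO system at intervention sites; the latter looks like a swap with the P4 row.
3. **Between-arm analysis in the protocol?** For the combined outcome, yes, through CAHPS items (7.1). For PCC-CA-6, no. The catch-all would give summaries within each arm, with no scoring rule and no comparison.
4. **In the SAP?** PCC-CA-6 is absent from the glossary, scoring (3.1.1), the questionnaire selection rules (3.1.3, which cover the QLQ-C30 and CAHPS), endpoints (3.6.1), analyses (3.6.3) and references. Communication is absent from the objective (2.2.1). It is also not among the qualitative and implementation objectives that 2.2.2 defers to separate SAPs.
5. **CAHPS in the SAP?** Frequencies only (3.6.3), where the protocol planned a mixed model.
6. **Disclosed?** No. Section 4 mentions neither the CAHPS change nor the absence of communication.

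Steps 3 to 5 together mean that, under the SAP, neither P3 instrument gives a modelled between-arm estimate.

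**Would a comparison be informative?** This is an illustration with borrowed inputs. From SAP 2.6: 1,200 patients, 52 practices, 85% evaluable at 3 months and ICC 0.055. The last two are stated there for physical function under the initial 1,000-patient design, not for PCC-CA-6. One PCC-CA-6 score, a two-sided 5% level and a baseline correlation of 0.5 to 0.6 are assumed.

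- Evaluable patients: 1,200 × 0.85 = 1,020
- Per practice: 1,020 / 52 = 19.6
- Design effect: 1 + (19.6 − 1) × 0.055 = 2.02
- Standard error of the difference, in SD units: √(4 × 2.02 / 1,020) = 0.089
- Difference detectable with 80% power: (1.96 + 0.84) × 0.089 = 0.25 SD
- With baseline adjustment, multiply by √(1 − r²): 0.25 × 0.866 = 0.22 SD at r = 0.5; 0.25 × 0.80 = 0.20 SD at r = 0.6

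**The case against.** The strongest reply is that the protocol does analyse the outcome it named. It listed one combined item, chose CAHPS to represent it, and wrote "patient satisfaction/communication as measured by CAHPS items will each be compared between arms". No rule requires every administered item set to have its own test, and the catch-all covers the remainder. This stands as far as the protocol goes. A reader might infer that neither document analyses communication, that PCC-CA-6 has no analysis of any kind, or that the trial cannot answer the question. The documents do not support these readings: 7.1 plans a CAHPS comparison, its catch-all would tabulate PCC-CA-6 within arms, and 5.5.1 has the data collected at baseline and follow-up in both arms. The reply does not rescue the SAP, which withdraws the CAHPS model and puts nothing in its place.

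A second reply is that the content of P3 is uncertain. Given the schedule tables and the SAP's reference to CAHPS items alone, the full short form may not have been administered in scorable form. This also stands, and it changes the remedy: if so, 5.5.1 is what needs correcting.

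A third is that the power figure describes a hypothetical test with another scale's ICC. That is correct. It shows that a comparison could be useful, not that omitting it did harm.

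A fourth is timing. SAP version 3 is dated September 30, 2022, and already cites the published secondary results, so an analysis added now may be post hoc. That limits how the result can be presented but is no reason to leave the data unplanned. The SAP's statement that exploratory analyses lie outside its scope does not settle the matter either, because the protocol calls this outcome secondary.

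**Conclusion.** The point holds in a limited form. PCC-CA-6 has no scoring rule, named endpoint or between-arm analysis in either document. Communication disappears from the SAP, and the CAHPS comparison that could have stood in for it becomes a frequency table, without an entry in Section 4. The consequence is that a named secondary outcome has no modelled, clustering-adjusted estimate for its communication part.

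The size is modest. No primary or key secondary endpoint is affected, and the gap can be closed without new data if the short form was given as 5.5.1 describes. The detectable difference of about 0.25 SD (0.20 to 0.22 SD with baseline adjustment) rests on the physical-function ICC and evaluability and on an assumed baseline correlation; treat it as illustrative. A reader might also infer that the outcome was dropped because of its results. Nothing in the documents shows that, or whether anyone had looked at the PCC-CA-6 data.

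**What to change.** - **SAP 3.1.1:** add the PCC-CA-6 scoring rule from its cited source (protocol reference 26).
- **SAP 3.6.1 and 3.6.3:** list the 3-month PCC-CA-6 score as a communication outcome. Compare arms with the mixed model of protocol 7.1 (cancer type, random practice effect, baseline score) and report the estimate with its confidence interval.
- **Protocol 7.1:** name PCC-CA-6 beside the CAHPS items as a measure of satisfaction/communication.
- **SAP Section 4:** record the addition, labelled post hoc if PCC-CA-6 data have already been seen. In the same entry, state that CAHPS items moved from a mixed model to frequencies, and why.
- **If the full short form was not administered or cannot be scored:** correct protocol 5.5.1 and say so in Section 4 instead.

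The cost is a few lines of text and one further model on data already collected. The downside is one more secondary comparison to report, possibly a post hoc one.
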